## Clinical Investigation Plan

### **10. EFFECTIVENESS ANALYSES**

#### **10.1. Primary Effectiveness Endpoint**

The primary effectiveness endpoint will compare the annualized HF hospitalization rate at 1 year in the study to the HF hospitalization rate in the year prior to enrollment.

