#### **12.1. Populations for Analysis**

**Safety Population:** The Safety Population consists of all subjects who received a Sensor implant or underwent the implant procedure but were never implanted, regardless of study completion status. All safety analyses will be performed on the Safety population.

Subjects who are found not to have an appropriately sized pulmonary artery branch and did not receive the Sensor implant will be considered ineligible for the study. However, these subjects will be followed for 30 days for safety and all safety related data for these subjects will be provided.

**Effectiveness Population:** The effectiveness population consists of all subjects who received a Sensor implant regardless of study completion status. All effectiveness analyses will be performed on the effectiveness population.

**Pooled Safety Population:** The Pooled Safety Population will consist of the Safety Population from this study and the Safety Population from other similar study(ies) (demonstrated to be poolable with this study) that have been combined to form a larger safety analysis population to permit more robust analyses.

**Pooled Effectiveness Population:** The Pooled Effectiveness Population will consist of the Effectiveness Population from this study and the Effectiveness Population from other similar study(ies) (demonstrated to be poolable with this study) that have been combined to form a larger effectiveness analysis population to permit more robust analyses.

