#### **12.2. Sample Size Considerations**

##### **Effectiveness Sample Size Determination**

For the primary effectiveness endpoint of HF hospitalization rate during 1 year, 250 subjects will provide greater than 90% power to meet the efficacy goal, using a one-sample, one-sided Poisson rate test with alpha of 0.025.

The HF hospitalization (HFH) rate for Control and Treatment groups at 1 year in Part 1 of the CHAMPION trial were 0.75 and 0.52 (HFH/patient-year), respectively. For this trial, HF hospitalization rates at 1 year will be compared to the rate observed in the trial subjects 1 year prior to enrollment (i.e., 1.0 or greater). Using a one-sample, 1-sided Poisson rate test with alpha of 0.025 (equivalent to 2-sided test at alpha of 0.05) (see table below), at least 149 subjects will provide >90% power to show a difference between a Treatment rate as high as 0.75 (conservative estimate) and the subject's own

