#### 12.8.1. Primary Effectiveness Endpoint

The primary time point for analyses is 12 months post-enrollment. The primary effectiveness endpoint will compare the annualized HF hospitalization rate parameter,  $\gamma$ , at 1 year versus the HF hospitalization rate in the year prior to enrollment using a one-sample, one-sided Poisson rate test. If the one-sided, upper 97.5% confidence interval for the PMS rate parameter is less than the rate in the year prior to enrollment, then the primary effectiveness endpoint will be met.

Mathematically stated, the primary effectiveness hypothesis is:

$$H_0: \gamma_{(12 \text{ month HF Hospitalization Rate})} \geq \gamma_{(\text{HF hospitalization rate in year prior to enrollment})}$$

$$H_a: \gamma_{(12 \text{ month HF Hospitalization Rate})} < \gamma_{(\text{HF hospitalization rate in year prior to enrollment})}$$

where  $\gamma_{(12 \text{ month HF Hospitalization Rate})}$  = the HF hospitalization rate parameter at 1 year in the PMS and  $\gamma_{(\text{HF hospitalization rate in year prior to enrollment})}$  = the HF hospitalization rate in the year prior to enrollment.

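### If subjects who die or leave in year 1 have higher HF hospitalization rates than those who stay, the primary comparison overstates the reduction, because the prior-year rate is not weighted by study follow-up

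*Combined protocol and SAP*

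**What the plan says.** Section 10.1 sets the primary effectiveness endpoint to "compare the annualized HF hospitalization rate at 1 year in the study to the HF hospitalization rate in the year prior to enrollment". Section 12.8.1 tests it with a one-sample, one-sided Poisson rate test. The condition for success is: "If the one-sided, upper 97.5% confidence interval for the PMS rate parameter is less than the rate in the year prior to enrollment".

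The rest of the plan fixes who and what enters each side:

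- **Who is analysed (12.1).** "The effectiveness population consists of all subjects who received a Sensor implant regardless of study completion status". Subjects who die or withdraw in year 1 are therefore included.
- **Prior-year events (8.1).** A 12-month HF hospitalization history before the baseline visit is collected for every subject.
- **Study-year rate (12.8.1).** It is called annualized, but no formula is given. The unit appears in 12.2, where the CHAMPION control and treatment rates at 1 year "were 0.75 and 0.52 (HFH/patient-year), respectively".
- **Incomplete follow-up (12.4).** Unresolved missing data are not imputed unless specified, and nothing is specified for the primary endpoint.
- **Death.** It enters only the supplemental mortality summary (12.8.2.1) and the supplemental HF-hospitalization-or-death comparison (12.8.2.2).

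**The concern.** The two rates average over the same subjects with different weights. A subject who dies at month 4 counts as one full year in the prior-year rate and one third of a year in a pooled study rate. If such subjects have more HF hospitalizations than the others, the study-year average leans toward low-rate subjects and the ratio drops below 1 with nobody improved.

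This is a shift in the estimate. A robust or overdispersed variance around the same pooled ratio would leave it in place, and better retention would not remove the part that comes from deaths. At stake is the accuracy of the headline reduction in HF hospitalizations in the study's only primary effectiveness test.

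**Working it through.** **1. The plan's own figure.** Section 12.2 plans the test "using a one-sample, one-sided Poisson rate test with alpha of 0.025". The critical count is the largest k with P(X ≤ k | n × 1.00) ≤ 0.025, and power is P(X ≤ k | n × 0.75). At n = 149 this gives k = 125, actual alpha 0.0247 and power 0.9016, as in the plan's table. At 250 subjects with full follow-up and a comparator of 1.0, k = 218, so a 12.8% observed reduction meets the rule. At 800 subjects k = 744, so 7.0% is enough.

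**2. Size of the shift, ignoring entry selection.** The documents give no year-1 mortality, exit rate or rate among leavers, so these inputs are assumptions:

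- m = share of subjects leaving in year 1;
- f = fraction of the year they contribute (0.5);
- R = their HF hospitalization rate divided by that of stayers.

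Hold each subject's rate fixed, with stayers at rate s:

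- prior-year rate = s[(1 − m) + mR]
- study rate = s[(1 − m) + mfR] / [(1 − m) + mf]

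For m = 0.15, R = 2 and a prior-year rate of 1.0:

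- s = 1/(0.85 + 0.30) = 0.8696, and leavers have 1.7391;
- events per subject = 0.85 × 0.8696 + 0.075 × 1.7391 = 0.8696;
- patient-years per subject = 0.85 + 0.075 = 0.925;
- study rate = 0.8696/0.925 = 0.940, an apparent reduction of 6.0%.

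Ratio of study rate to prior-year rate, with no subject changed:

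| R | m = 10% | m = 15% | m = 20% |
|---|---|---|---|
| 0.67 | 1.016 | 1.024 | 1.031 |
| 1 | 1.000 | 1.000 | 1.000 |
| 1.5 | 0.977 | 0.968 | 0.960 |
| 2 | 0.957 | 0.940 | 0.926 |
| 3 | 0.921 | 0.894 | 0.873 |

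Earlier exit enlarges the effect: with f = 0.25, m = 15% and R = 2, it is 9.4%.

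**3. Against the success rule, still ignoring entry selection.** With 800 subjects, m = 15% and R = 2, follow-up is 800 × 0.925 = 740 patient-years. The exact upper limit for x events in T patient-years is χ²(0.975; 2(x + 1))/(2T).

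- Prior-year rate 1.0 (the plan's planning value): about 696 events, upper limit 1.013. The rule is not met at the expected count. The probability of meeting it is 0.37, against 0.024 when R = 1.
- Prior-year rate 1.5 (an assumption): about 1043 events, rate 1.41, upper limit 1.498. The rule is only just met, with probability 0.51.

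**4. With entry selection.** Inclusion criterion 4 in 6.1 requires at least one HF hospitalization in the prior 12 months. The simulation used 800 subjects, gamma-distributed rates with pre-selection mean 1.0 or 1.5 and CV 0.5 to 1.0, exits of 10% to 20% with hazard proportional to the subject's rate, and no change in any subject's rate.

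| Comparator | Ratio | Rule met |
|---|---|---|
| Unweighted, as planned | 0.66 to 0.82 | essentially 100% of runs |
| Follow-up-weighted | 0.66 to 0.83 | at least 99.8% of runs |

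Within a scenario, weighting moves the ratio by about 0.3 to 4 percentage points. Regression to the mean after selecting on a prior event accounts for the rest.

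**5. Does weighting remove the shift?** In the step 2 example the weighted prior-year rate is (0.85 × 0.8696 + 0.075 × 1.7391)/0.925 = 0.940, equal to the study rate. Simulated without entry selection, the mean ratio with the weighted comparator is 1.00.

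**The case against.** **The documents do not establish the direction.** A reader might infer that unequal weights alone produce a reduction. They do not: the bias is exactly zero at R = 1 and goes against the device at R below 1. Section 3.1 lists frequent hospitalization and high mortality together as features of heart failure, which makes R above 1 plausible for deaths, but gives no figure. The case is weaker for the exits in 8.7, such as withdrawn consent, noncompliance and loss to follow-up. This objection stands, and the point is conditional for that reason.

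**The formula is not defined.** An unweighted mean of subject-level annualized rates would remove the mismatch. The Poisson rate test and the per-patient-year unit point to the pooled reading, but the plan does not say so. This stands as a limit on confidence and as a reason to write the definition down.

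**The effect is small beside the planned difference.** It is: about 6% in the central case against a planned 25%. The rule, however, asks for any reduction, and at 800 subjects about 7% suffices.

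**Deaths are not hidden.** If all leavers in the central case are deaths, the HF-hospitalization-or-death rate is about 0.94 + 0.15/0.925 = 1.10, above the prior-year 1.0. That supplement more than offsets the effect there, but it does not decide the primary endpoint and uses the same unweighted comparator.

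**Conclusion.** The point holds in conditional form. Read as a pooled rate, the study rate is weighted by follow-up, the prior-year rate is not, and nothing in the primary analysis corrects for it. If leavers have higher rates, the reduction is overstated by about 2% to 13% over the assumed ranges, or 6% at 15% leaving and a rate ratio of 2, ignoring entry selection.

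Two stronger readings are not supported. The first is that this mismatch decides whether the endpoint is met. Under the trial's own entry rule, the simulated decision is the same with and without the correction, because regression to the mean, a separate issue, dominates. The second is that the correction restores the nominal error rate. Even without entry selection, the rule with a weighted comparator is met falsely in about 6% to 10% of runs rather than 2.5%, because 12.8.1 still treats the prior-year rate as a known constant.

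Severity is moderate: a real and avoidable bias in the primary effect estimate. Confidence is medium, since the exit share, timing and rate ratio are all assumed.

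**What to change.** In 12.8.1, and likewise in 12.8.2.2 and 12.8.2.5:

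1. Define the annualized rate as total HF hospitalizations over total patient-years in year 1 (adding deaths to the count in 12.8.2.2).
2. Compare it with an exposure-weighted prior-year rate, Σ(prior-year count_i × t_i)/Σt_i, where t_i is the subject's year-1 follow-up in years.
3. Alternatively, for HF hospitalizations, estimate the rate ratio from a Poisson model conditional on subject, with log follow-up time as offset. It solves a different equation from item 2, so one of the two should be named as primary. It also avoids treating the prior-year rate as a known constant.
4. Report the unweighted comparison as a sensitivity analysis.

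The prior-year counts are already collected, and follow-up time is already needed to annualize the study rate. The cost is SAP wording, a few lines of code and a slightly less favourable stated reduction: in the example with a prior-year rate of 1.50, the comparator becomes 1.41. Neither option addresses regression to the mean, which needs its own treatment.

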#### 12.8.2. Supplemental Analyses

##### 12.8.2.1. Mortality

The mortality rate over 1 year in study will be reported. Plotting and analysis of survival data will be displayed using Kaplan-Meier methods.

##### 12.8.2.2. HF Hospitalization or Death

The annualized HF hospitalization or death rate parameter,  $\lambda$ , at 1 year will be compared to the HF hospitalization rate in the year prior to enrollment using a one-sample, one-sided Poisson confidence

## Clinical Investigation Plan

interval. If the one-sided, upper 97.5% confidence interval for the PMS rate parameter is less than that in the year prior to enrollment, then the hypothesis will be met.

Mathematically stated, the hypothesis is:

$$H_0: \lambda_{(12 \text{ month HF Hospitalization or Death Rate})} \geq \lambda_{(\text{HF hospitalization rate in year prior to enrollment})}$$

$$H_a: \lambda_{(12 \text{ month HF Hospitalization or Death Rate})} < \lambda_{(\text{HF hospitalization rate in year prior to enrollment})}$$

where  $\lambda_{(12 \text{ month HF Hospitalization or Death Rate})}$  = the HF hospitalization or death rate parameter at 1 year in the PMS and  $\lambda_{(\text{HF hospitalization rate in year prior to enrollment})}$  = the HF hospitalization rate in the year prior to enrollment.

### 12.8.2.3. Patient Compliance

Patient device usage over the course of the trial will be examined. The total number of PA pressure readings taken will be reported as a percentage of patient days at home.

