## Clinical Investigation Plan

### 2. PROTOCOL SYNOPSIS

Sponsor:	St. Jude Medical, Atlanta, GA
Protocol Title:	CardioMEMS HF System OUS Post Market Study
Document Control Number:	SJM-CIP-10147
Device:	The CardioMEMS™ HF System consists of a wireless, battery-less pressure sensor implanted into the pulmonary artery and an external electronics that powers and communicates with the sensor and transmits pulmonary artery pressure waveforms and measurements to a secure website for Investigator review and patient management.
Purpose:	The purpose of this Post Market Study (PMS) is to evaluate the use of the CardioMEMS™ HF System in patients with Class III Heart Failure in a real-world setting.
Objective:	The objective of this PMS is to confirm safety and effectiveness in a real-world setting.
Study Population:	
Adults with New York Heart Association (NYHA) Class III Heart Failure (HF) who have experienced a heart failure hospitalization within the past 12 months.
 
The patients will serve as their own historical controls for effectiveness (1 year prior to implantation).
 
All subjects who sign the informed consent form and satisfy the inclusion/exclusion criteria.
 
Ejection fraction data must be taken within the last 6 months or prior to implantation.

Study Design:	
This is a prospective, multi-center, open-label trial conducted in centers located outside of the United States (US).
 
All subjects who sign the informed consent form and satisfy the inclusion/exclusion criteria will be enrolled into the CardioMEMS™ HF System PMS and will be scheduled for follow-up visits at 1 month and every 6 months for 2 years.
 
Following sensor implant and hospital discharge, subjects will take PA pressure measurements on a daily basis, or as directed by the investigator. These measurements will be automatically transmitted to the secure patient database (Merlin.net website).

Timeline:	Study visits will be scheduled at Month 1, Month 6, and every 6 months thereafter for 2 years or until study termination.

*This confidential document is the property of Abbott and shall not be reproduced, distributed, disclosed or used without the express written consent of Abbott*

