### **5. STUDY DESIGN**

This is a prospective, multi-center, open-label clinical trial to be conducted up to 85 sites in centers located outside of the US.

Subjects who sign the informed consent form and meet the eligibility criteria at the Baseline visit will be eligible for the trial. Subjects will undergo the study-related procedures, including clinical laboratory measurements and body mass index (BMI) calculation. Note that for study related procedures/visits Investigator refers to the Principal Investigator or designee.

Eligible subjects will be scheduled for the Implant procedure (PA sensor implant in conjunction with a RHC procedure).

Subjects must also have an appropriately sized ( $\geq 7$ mm diameter) pulmonary artery branch identified by a selective pulmonary angiogram prior to Sensor implant. Subjects who do not meet this inclusion criteria will be documented as consented not implanted and will be followed for 30 days for safety.

Prior to hospital discharge, subjects will be trained on the home monitoring system and instructed to take pulmonary artery pressure measurements daily or as directed by their physician. Subjects will be supplied with a patient implant identification card, a Patient System Manual, and a Helpline phone number.

After discharge, the subject will take PA pressure measurements at home, as directed by the investigator, utilizing the CardioMEMS HF System. These measurements will be transmitted via modem to a secure data base. Patient compliance will be monitored by the sponsor and reported to the Investigator.

The Investigator or designee will review the PA pressure measurements transmitted from the home monitoring unit. Pressure thresholds are automatically set as described in Appendix C. These threshold notifications are intended to guide the Investigator to review the Merlin.net website. If the PA pressures are elevated or low, the Investigator or designee should make medication changes according to the guidelines in Appendix C. The Investigator or designee will review the PA pressure measurements on a weekly basis at a minimum and appropriately utilize the information obtained to assist in the clinical management of subjects. Weekly logins to the database will be monitored by the sponsor. Reminders will be sent to the clinical sites if there are no logins noted during the course of a 7 day window. Clinical and technical support will be available to the Investigator as needed.

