## Clinical Investigation Plan

### **8. STUDY PROCEDURES**

All subjects will be followed for 2 years. A subject is considered to have successfully completed the study upon completion of the 2 year visit (see Appendix A for the Schedule of Events).

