### 8.5. Subject Home PA Pressure Readings

Following the sensor implant procedure, subjects will be instructed on how to take their own pulmonary artery pressure measurements, utilizing the CardioMEMS™ HF System. Subjects will provide returned demonstration on: setting up the unit, connecting the system to a phone line, proper positioning for obtaining the optimum sensor signal, taking and transmitting the daily pressure measurements. The unit will transmit the data to a database using the system's modem.

The home measurements will be taken while the subject is lying down (supine) in bed positioned on a padded, flat antenna. It is recommended that subjects obtain home measurements in a supine position however, if the subject is unable to lie flat, measurements can be obtained in a sitting or reclined position. It is important the anatomical position is consistent for every measurement.

*This confidential document is the property of Abbott and shall not be reproduced, distributed, disclosed or used without the express written consent of Abbott*

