##### 9.1.2. Sensor Failure Criteria

A Sensor failure occurs when no readings can be obtained from it after troubleshooting the system to rule out any problems with the external electronics.

*This confidential document is the property of Abbott and shall not be reproduced, distributed, disclosed or used without the express written consent of Abbott*

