##### **10.2.3. Patient Compliance**

Patient device usage over the course of the trial will be examined.

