### Tests for One Proportion – Freedom from Sensor Failures

Numeric Results for Testing One Proportion using the Exact Test

Alternative Hypothesis: One-Sided (H0: P ≤ P0 vs. H1: P > P0)

Power*	n	Proportion		Difference	Target Alpha	Actual Alpha*	Reject H0
		Given H0	Given H1				
0.90193	292	0.9000	0.9500	0.0500	0.0250	0.0242	273
0.91154	193	0.9000	0.9600	0.0600	0.0250	0.0242	182
0.91132	127	0.9000	0.9700	0.0700	0.0250	0.0250	121
0.90879	85	0.9000	0.9800	0.0800	0.0250	0.0245	82
0.96665	70	0.9000	0.9900	0.0900	0.0250	0.0242	68

\* Power and actual alpha were computed using binomial enumeration of all possible outcomes.

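### Patient compliance divides a count of readings by a count of home days with no limit of one per day, so repeat readings offset missed days and the figure can exceed 100%

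*Combined protocol and SAP*

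**What the plan says.** The rule appears twice in the same words, in the Synopsis (Statistical Considerations) and in section 12.8.2.3 under the heading Patient Compliance: "The total number of PA pressure readings taken will be reported as a percentage of patient days at home". Section 10.2.3, under the same heading, gives only the general aim: "Patient device usage over the course of the trial will be examined".

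On how often subjects should read, the Synopsis says that "subjects will take PA pressure measurements on a daily basis, or as directed by the investigator". Section 5 says that they are "instructed to take pulmonary artery pressure measurements daily or as directed by their physician". Section 8.5 includes in the home training "taking and transmitting the daily pressure measurements". These sentences tell subjects what to do; none is a rule for counting readings in the analysis.

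Appendix F defines neither compliance nor days at home. Section 12.8, which governs the effectiveness and supplemental analyses, provides for N, mean, standard deviation, median, minimum and maximum as appropriate. No target, hypothesis or significance level is attached to compliance.

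**The concern.** A percentage headed compliance, with home days as its base, is likely to be read as the share of home days on which the subject took a reading. The rule does not guarantee that, because its numerator and denominator are in different units. A second reading on Tuesday cancels a missed reading on Monday. If the totals are pooled, a frequent reader cancels someone who has stopped reading. A value near 100% could then come from steady daily use or from a mixture of gaps and repeats, and the reported figure would not tell them apart.

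What is at stake is interpretation. Investigators act on the transmitted pressures, so the extent of use is background to the effectiveness result. No formal conclusion of the study depends on it.

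**Working it through.** The plan states no compliance figure or target, so there is nothing to reproduce. The check is algebra on the stated rule, followed by examples whose reading patterns are assumptions.

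**Identity.** For readings taken on home days, let H be home days, D the home days with at least one reading, R total readings, and E = R − D the extra same-day readings. Then

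- figure as written = 100 × R/H = 100 × D/H + 100 × E/H;
- coverage (share of home days with a reading) = 100 × D/H.

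The two differ by exactly the number of extra readings per 100 home days. They agree when E = 0.

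**When the figure passes 100%.** This happens once 100 × E/H exceeds 100 minus coverage:

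| Coverage | Home days per extra reading at which the figure reaches 100% |
|---|---|
| 80% | 100/(100 − 80) = 5 |
| 90% | 100/(100 − 90) = 10 |
| 95% | 100/(100 − 95) = 20 |

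**Range at an assumed 90% coverage.**

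| Extra readings (assumed) | Figure as written |
|---|---|
| none | 90.0% |
| one per 30 home days | 90 + 100/30 = 93.3% |
| one per 14 home days | 90 + 100/14 = 97.1% |
| one per 7 home days | 90 + 100/7 = 104.3% |

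**Offset within one subject (assumed patterns, 365 home days).**

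- None on 73 days, two on 73, one on 219: readings 2 × 73 + 219 = 365, so 365/365 = 100% as written; coverage 292/365 = 80%.
- Two on 182 days, none on 183: 364/365 = 99.7% as written; coverage 182/365 = 49.9%.
- One every day plus one repeat on 30 days: 395/365 = 108.2% as written; coverage 100%.

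**Offset across subjects (assumed, equal home days).** Subject A reads once on 60% of days: 60%. Subject B reads once on 60% and twice on 40%: 0.60 + 2 × 0.40 = 140%. Pooled as written: (60 + 140)/2 = 100%. Pooled coverage: (60 + 100)/2 = 80%.

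**End of the denominator.** Section 9.1.2 says "A Sensor failure occurs when no readings can be obtained from it after troubleshooting the system", and section 8 says "All subjects will be followed for 2 years". No stopping rule for home days is given, so read literally, days after a sensor failure count as missed. If a fraction f of sensors fails evenly over 24 months, and deaths, exits and hospital days are ignored, f/2 of home days are lost. The section 12.3 table headed "Freedom from Sensor Failures" includes planning rates of 0.99 and 0.95. With these as assumed inputs, a true 90% would read 90 × (1 − 0.005) = 89.55% or 90 × (1 − 0.025) = 87.75%. This is small and runs in the opposite direction to repeat readings.

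**The case against.** The strongest reply is that the measure is open about what it is. Section 10.2.3 calls it device usage, and the rule names its numerator and denominator. Every statement about frequency points to a daily reading or one set by the physician, and no section asks for more than one home reading a day. If subjects read at most once a day, the ratio is the share of days covered and nothing is distorted. That stands as a limit on size: the repeat patterns above are illustrations. It does not remove the point, because an instruction to read daily does not stop a second reading from being counted. If one reading a day is what is meant, writing it into the rule changes no result.

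A second reply is that section 12.8 already provides for minimum, maximum and median, so subjects at 60% and 140% would be visible. That holds if the ratio is formed per subject, although a total over patient days can equally be read as one pooled ratio. Subject-level summaries in any case do not undo the offset within a subject.

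A reader might also infer more than the documents support:

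- That hospital and clinic readings inflate the figure. They are permitted, but home readings are the natural reading of a measure based on days at home.
- That the figure fails because some subjects may be directed to read less than daily. The documents do not say how many would be, and counting days with a reading would leave that limitation in place.
- That sensor failure could depress the figure as it would with 10% failing. The 0.90 in the sensor table is the null value that the safety test must exceed, not an expected rate.

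**Conclusion.** The point holds as a property of the stated rule. The figure is coverage plus extra same-day readings per 100 home days, so repeats offset missed days and values above 100% are possible. This follows from the wording and needs no assumption beyond counting readings taken on home days.

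The practical size cannot be determined. The documents give no repeat-reading frequency, and the effect is zero if subjects never read more than once a day. A reader might infer that the reported compliance will be materially overstated; the documents do not support that. They show only that the rule allows it and would not reveal it.

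The measure is descriptive and supplemental. No hypothesis, performance criterion, alpha or sample size changes. This is a cheap improvement.

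**What to change.** In the Synopsis and section 12.8.2.3, define compliance for each subject as the number of home days with at least one reading, divided by days at home while in the study, with the count of days ending at sensor failure, explant, exit or death. Summarise the subject-level percentages with the statistics already listed in section 12.8. Keep total readings per home day as a separate measure, labelled as usage.

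The cost is a short definition in two places and a little more analysis work. Home readings are already transmitted automatically to the database, hospitalizations and deaths are already collected, and the Kaplan-Meier display of the safety endpoints in section 12.7.1 already needs sensor-failure dates. The definition does not depend on flagging where a reading was taken, which the documents do not show to be recorded.

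The downside is that the percentage may look less favourable. On the same days, the share covered is never higher than the ratio as now written. Ending the count at sensor failure works the other way for the subjects affected.
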